#### 4.3.2.1 Dose escalation criteria and Dose Limiting Events

Dose escalation will be managed according to review of available and emerging data on the subjects administered ATIMP top date and the occurrence, if any, of DLE's or medically important events. An SDMC will review data from a minimum of 6 weeks of follow up from each cohort of participants (at least one older child, 11-15 years of age per cohort), before recommending the next dose to be assessed in a further cohort of participants or to additional participants at the same dose level.

A DLE is defined as any of the below occurring during the 6 weeks following administration, at least possibly related to the ATIMP, not surgery alone:

- A reduction in visual acuity by 15 ETDRS letters or more that fails to resolve to within 15 letters of baseline in a 4-week period once prophylactic treatment commences
- Severe unresponsive inflammation (defined below)\*
- Infective endophthalmitis
- Ocular malignancy
- Grade III or above non-ocular SUSAR (see section 5.11.3)

\* Severe unresponsive inflammation will be defined according to the Standardisation of Uveitis Nomenclature (SUN) Working Group grading system (Jabs *et Al.* 2005) i.e.

- anterior chamber cells 3+ (26-50 cells in a field size of 1mm x 1-mm slit-beam), or
- anterior chamber flare 3+ (marked, iris and lens details hazy), or
- vitreous haze 3+ (Ophthalmology 1985; 92:467-71)

that fails to improve by 2 steps (or to grade 0) during a 6-week period.

Review of safety data will be undertaken by the SDMC prior to each dose escalation.

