## 5.5 Outcomes

### 5.5.1 Primary Outcomes

The primary outcome is defined as any of the below occurring during the 6 weeks following administration, at least possibly related to the ATIMP, not surgery alone:

- Reduction in visual acuity by 15 ETDRS letters or more that fails to resolve to within 15 letters of baseline in a 4-week period once prophylactic treatment commences
- Severe unresponsive inflammation
- Infective endophthalmitis
- Ocular malignancy
- Grade III or above non-ocular SUSAR (see section 5.11.3)

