**CNGA3/CNGA3 Gene Therapy trial for Achromatopsia**

**5.11.3.5 Investigator responsibilities relating to safety reporting**

The Investigator will assume overall responsibility for evaluating and reporting adverse events. In urgent situations, a member of the trial team may report on their behalf, while making every effort to discuss the event with them. The investigator may consult the study medical monitor for advice, but they will assume overall responsibility for the evaluation, assignment of clinical significance and reporting of adverse events. All non-serious AEs and ARs, whether expected or not, should be recorded in the participant’s medical notes, including all events observed following ATIMP administration, and in the eCRF. These should be entered on to the database according to the timelines defined in the CNGA3 Gene Therapy trial for Achromatopsia Data Management Plan to allow appropriate monitoring by the CMT. SAEs and SARs should be notified to PV Service Provider immediately the investigator becomes aware of the event (in no circumstance should this notification take longer than 24 hours).

Clinically significant abnormalities in the results of objective tests will also be recorded as adverse events. If the results are not expected as part of disease or surgery these will also be recorded as unexpected. There are currently no expected events associated with the ATIMP.

All serious adverse events will be recorded in the hospital notes and the eCRF. Adverse events will be recorded with clinical symptoms and accompanied with a simple, brief description of the event, including dates as appropriate. All adverse events will be recorded until the end of the trial (refer to Section 5.6.3 for definition), or until pregnancy outcome in the case of pregnancy. All SAEs will be recorded, fully investigated and appropriately managed until resolution or stabilisation and CI sign off.

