#### 5.11.3.5.3 Causality

Causality will be assessed in terms of both the ATIMP and the surgical procedures. Based on all available information at the time of completion of the case report form, the investigator must assess the causality of all serious events or reactions. It is of importance in this trial to capture and differentiate events related to:

- The ATIMP administration surgery
- The ATIMP

The differentiated causality assessments will be captured in the trial specific CRF and SAE form. If the event is related to the ATIMP, definitions in Table 5 will be used to capture the information. Any event that is only related to the ATIMP administration surgery will be classified as an Adverse Event. The study medical monitor is available 24/7 to provide any advice as required

Table 5: Causality definitions

Relationship	Description	Event Type
Unrelated	There is no evidence of any causal relationship	Unrelated SAE
Unlikely to be related	There is little evidence to suggest that there is a causal relationship (e.g., the event did not occur within a reasonable time after administration of the trial medication). There is another reasonable explanation for the event (e.g., the participant's clinical condition or other concomitant treatment)	Unrelated SAE
Possibly related	There is some evidence to suggest a causal relationship (e.g., because the event occurs within a reasonable time after administration of the trial medication). However, the influence of other factors may have contributed to the event (e.g., the participant's clinical condition or other concomitant treatment)	SAR
Probably related	There is evidence to suggest a causal relationship and the influence of other factors is unlikely	SAR
Definitely related	There is clear evidence to suggest a causal relationship and other possible contributing factors can be ruled out.	SAR

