#### 1. INTRODUCTION

This Statistical Analysis Plan (SAP) specifies definitions of analysis sets, key derived variables, and statistical methods for the analysis of safety and efficacy data for the Phase I/II CNGA3 study (MGT012). This SAP is based on the protocol of study MGT012, v 6.0 16April2021. Titles, mock-ups and programming instructions for all statistical outputs (tables, figures, and listings) are provided in a separate document.

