#### 2. OUTCOME DEFINITIONS

### 2.1. Primary Safety Outcome

The primary safety outcome is defined as the absence/presence of any of the below events occurring during the 6 weeks following administration, at least possibly related to the ATIMP, not surgery alone:

- Reduction in visual acuity by 15 Early Treatment Diabetic Retinopathy Study (ETDRS) letters or more
- Severe unresponsive inflammation (defined in Section 4.2 of the protocol)

- Infective endophthalmitis
- Ocular malignancy
- Grade III or above non-ocular suspected unexpected serious adverse reaction (SUSAR) (Protocol MGT006, Section 5.11.3.4.2 Severity or Grading of Adverse Events).

This is the same criteria as the dose limiting event in the dose escalation phase.

Overall safety will be assessed for 6 months after the intervention in this study, and a further 4.5 years in a separate long-term follow-up study (Protocol MGT007).

The adverse events preferred terms are identified in Attachment 2.

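### SAP 2.1 drops the protocol's 4-week non-resolution clause from the acuity component of the primary safety outcome, yet says the criteria match the DLE

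*SAP*

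**What the plan says.** The protocol defines the acuity item in the same way in its summary (1.3), primary objective (4.2.1), DLE definition (4.3.2.1), primary outcomes (5.5.1) and primary analysis (5.10.3.2). In 5.5.1 it reads "Reduction in visual acuity by 15 ETDRS letters or more that fails to resolve to within 15 letters of baseline in a 4-week period", and the clause goes on to date the four weeks from the start of prophylactic treatment. Events count when they occur in the 6 weeks after administration and are "at least possibly related to the ATIMP, not surgery alone".

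SAP 2.1 keeps the 6-week period and the attribution condition, but its acuity item is only "Reduction in visual acuity by 15 Early Treatment Diabetic Retinopathy Study (ETDRS) letters or more". It then states "This is the same criteria as the dose limiting event in the dose escalation phase" and adds "The adverse events preferred terms are identified in Attachment 2". In Attachment 2 the acuity row is the single preferred term Visual acuity reduced, with no letter threshold and no duration.

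SAP 5.1 reports the proportion with the primary safety outcome, with a 95% interval, by age group, dose level and overall.

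**The concern.** The missing clause separates a lasting loss from a passing one. Protocol 5.11.3.5.4 explains that some temporary loss of acuity is expected after this surgery, and that safety was therefore defined by the absence of an event with a substantial and sustained effect on vision. The SAP's item has lost the sustained part.

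The SAP's inflammation item refers back to protocol section 4.2, so its failure-to-improve condition carries over. The acuity item has no such reference. The only link is the sentence claiming equivalence with the DLE, which is wrong for the item as listed.

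At stake is the reported primary result. The SAP proportion and the protocol's DLE count could differ for the same participants, although the SAP presents them as one quantity.

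**Working it through.** **Step 1. Compare the definitions.** Take a measured loss of 15 letters or more in the 6-week period.

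| Course and attribution | Protocol event | SAP 2.1 event as listed |
|---|---|---|
| Does not resolve in 4 weeks; at least possibly ATIMP-related | Yes | Yes |
| Resolves in 4 weeks; at least possibly ATIMP-related | No | Yes |
| Attributed to surgery alone | No | No |

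The definitions differ only in the second row. Every protocol event is also a SAP event, so the omission by itself can only raise the count.

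**Step 2. Size.** The plan gives no figure to reproduce and no rate of transient loss. The counts below are assumptions that show what one reclassified participant does.

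Inputs: n = 18 (maximum in protocol 5.7) and n = 3 (initial cohort size in protocol 4.3).

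- Exact (Clopper-Pearson) two-sided 95% upper limit: for 0/n, 1 − 0.025^(1/n); for 1/n, the 97.5th percentile of Beta(2, n − 1).
- SAP 5.1 interval: p ± [1.96 × √(p(1 − p)/n) + 1/(2n)], here truncated to 0–100%. The truncation is my assumption.

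| Count | Proportion | Exact upper limit | SAP 5.1 upper limit |
|---|---|---|---|
| 0/18 | 0% | 18.5% | 1/36 = 2.8% |
| 1/18 | 5.6% | 27.3% | 5.6 + 1.96 × 5.4 + 2.8 = 18.9% |
| 0/3 | 0% | 70.8% | 1/6 = 16.7% |
| 1/3 | 33.3% | 90.6% | 33.3 + 1.96 × 27.2 + 16.7 = 103.3%, cut to 100% |

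On the exact scale, one participant moves the overall upper limit by 27.3 − 18.5 = 8.8 percentage points. The larger jump under the SAP's method (2.8% to 18.9%) partly reflects its normal approximation, which is a separate matter. If three participants had transient, possibly related losses, the SAP wording would give 3/18 = 16.7% (exact 3.6% to 41.4%) and the protocol wording 0/18.

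**Step 3. The clock.** Protocol 5.4.1.5 starts oral steroid one week before dosing and continues it for four weeks after. The start of prophylactic treatment can therefore be read in several ways:

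- From the first oral dose, four weeks end 4 − 1 = 3 weeks after dosing, between the W2 and W4 visits.
- From dosing, they end at W4.
- From onset of the loss, a loss first seen at W4 runs to W8, and protocol Table 2 has no visit between W6 and W12.

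Take a loss seen at W2 that has recovered by W4. It is resolved if the clock runs from onset or from dosing. If the clock runs from the first oral dose, the scheduled visits cannot settle it. Copying the clause back unchanged would leave this open.

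**Step 4. Are the data there?** Protocol Table 2 schedules acuity at D1, D3, W1, W2, W4 and W6 (six post-dose tests) and at three baseline visits. The item can be derived from letters already collected.

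**The case against.** The best defence is that the equivalence sentence imports the protocol's DLE definition, so a programmer would apply the full clause. That is a possible intention. But the SAP then says two different things, and the listed criterion is the explicit one. The SAP also says "Titles, mock-ups and programming instructions for all statistical outputs (tables, figures, and listings) are provided in a separate document"; the derivation may be correct there. That is unknown, and it would not correct SAP 2.1.

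It is also fair that any single event matters in a trial this small, and that no frequency is shown. The size above is one of sensitivity, not a predicted error.

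Two stronger readings are tempting, and the documents do not support them.

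*That the adverse event term alone decides the acuity component.* SAP 2.1 keeps the 15-letter threshold. Attachment 2 has no row for the non-ocular SUSAR component and gives no grade for inflammation, so it reads as a term list used alongside the criteria. SAP 3.4 lets additional visits inform clinically important outcomes. The protocol also requires that "Clinically significant abnormalities in the results of objective tests will also be recorded as adverse events". What remains is that no stated rule links measured letters to the term.

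*That losses attributed to surgery disappear from view.* Excluding them from the primary count is the protocol's own definition. SAP 5.2 tabulates all treatment-emergent events by preferred term and by relationship to ATIMP and to surgery, with listings. SAP 6.1 plots each participant's treated and untreated eye over time. On causality, the protocol says "The differentiated causality assessments will be captured in the trial specific CRF and SAE form". None of these outputs applies the 15-letter criterion to measured acuity, so the view is partial. That justifies an optional addition, not a finding of error.

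**Conclusion.** The point holds as an inconsistency between SAP and protocol on one component of the primary outcome. SAP 2.1 omits the non-resolution clause, and its statement of equivalence with the DLE is therefore wrong for acuity. Taken alone, the omission can only over-count, and only through transient losses judged at least possibly related to the ATIMP. One such participant changes 0% to 5.6% overall (exact upper limit 18.5% to 27.3% at n = 18), or 0% to 33.3% in a cohort of three.

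This assumes that the SAP is programmed as its list reads and that the shells do not already supply the clause.

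A reader might also infer that dose escalation rests on the wrong criterion. The documents do not show that: escalation follows the DLE definition in protocol 4.3.2.1, which keeps the clause, and the SDMC also weighs other clinically relevant events. The effect is on the reported primary result.

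**What to change.** 1. Restore the non-resolution clause in SAP 2.1.
2. State the day on which the 4-week clock starts, and what is done when the deadline falls between visits. Align the protocol wording, because the ambiguity begins there.
3. Derive the acuity item from measured ETDRS letters against the SAP 3.2 baseline (mean of the planned baseline tests). Say that this baseline applies here, since SAP 3.2 words the mean for efficacy parameters. Use every post-dose acuity test, not only the one kept per visit window. Keep Visual acuity reduced as a cross-check and reconcile differences.
4. Optionally, add to the SAP 5.1 listing a labelled supplementary count of participants meeting the measured criterion regardless of attribution, with recorded ATIMP and surgery causality.

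The cost is one clause, one agreed clarification in the protocol, one derivation and, if wanted, one row and a listing. No new data are needed. The clarification takes the most effort, since it settles a protocol question. The optional count will look less favourable: protocol 5.11.3.5.4 accepts surgical loss to hand movements for up to 8 weeks as expected, longer than the 6-week outcome period. It must not replace the primary count.

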## 4.2 Objectives

### 4.2.1 Primary Objective

The primary research objective is to assess the safety of an AAV2/8 vector for *hCNGA3* gene replacement in the retina. Safety is defined as:

Safety is defined as the absence of an ATIMP-related:

- Reduction in visual acuity by 15 ETDRS letters or more that fails to resolve to within 15 letters of baseline in a 4-week period once prophylactic treatment commences
- Severe unresponsive inflammation (defined below)
- Infective endophthalmitis
- Ocular malignancy
- Grade III or above non-ocular SUSAR (see section 5.11.3)

Severe unresponsive inflammation will be defined according to the Standardisation of Uveitis Nomenclature (SUN) Working Group grading system (Jabs *et Al.* 2005) i.e.

- anterior chamber cells 3+ (26-50 cells in a field size of 1mm x 1-mm slit-beam), or
- anterior chamber flare 3+ (marked, iris and lens details hazy), or
- vitreous haze 3+ (Ophthalmology 1985; 92:467-71)

that fails to improve by 2 steps (or to grade 0) during a 6-week period.

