### **(i) Clinical assessment of intraocular inflammation**

The degree of intraocular inflammation will be assessed by slit-lamp biomicroscopy at each time point. A temporary intraocular inflammatory response is expected following vitrectomy surgery. This is typically evident clinically on slit-lamp biomicroscopy as 'flare' and cells in the anterior chamber and can be of moderate (2+ cells) intensity. The degree of intraocular inflammation is expected to decline over the course of the first 4 weeks following the surgical procedure, at which time the routine topical and systemic immunosuppression will be discontinued. Prolonged or severe intraocular inflammation, or deterioration in visual acuity that may be related to intraocular inflammation, will be investigated and managed conventionally with further topical and/or systemic immunosuppression.

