# 2.2. Efficacy Outcomes

As listed in the protocol (Section 5.6 Trial Assessments), the following efficacy outcomes will be analyzed or summarized depending on the amount of data collected:

- Visual acuity (VA)
- Contrast sensitivity
- Reading assessments
- Color vision assessments
- Static perimetry
- Full field stimulus testing (FST)
- Ocular examination
- Fundus photography
- Spectral domain optical coherence tomography (SD-OCT)
- Adaptive optics imaging
- Fundus autofluorescence
- Photoaversion (PA)
- Electroretinography (ERG)
- Quality of life (QoL) as measured by the Impact of Visual Impairment (IVI) questionnaire adult (IVI-A) and child (IVI-C) versions, and the EQ5D-5L and EQ5D-Y
- Photoaversion questionnaire.

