# ATTACHMENT 2: LIST OF ADVERSE EVENT PREFERRED TERMS FOR THE PRIMARY SAFETY OUTCOME

Adverse Event Category	Preferred Terms
Endophthalmitis	Endophthalmitis
Ocular malignancies	Carcinoma in situ of eye
_	Extraocular retinoblastoma
	Malignant neoplasm of choroid
	Malignant neoplasm of conjunctiva
	Malignant neoplasm of cornea
	Malignant neoplasm of eye
	Malignant neoplasm of lacrimal duct
	Malignant neoplasm of lacrimal gland
	Malignant neoplasm of orbit
	Malignant neoplasm of retina
	Retinoblastoma
	Ocular cancer metastatic
	Malignant neoplasm of eyelid
	Congenital retinoblastoma
Ocular inflammation	Anterior chamber cell
	Anterior chamber fibrin
	Anterior chamber flare
	Anterior chamber
	inflammation
	Chorioretinitis
	Cyclitic membrane
	Cyclitis
	Endophthalmitis
	Eye inflammation
	Hypopyon
	Immune-mediated uveitis
	Iridocyclitis
	Iritis
	Non-infectious
	endophthalmitis
	Ocular vasculitis
	Panophthalmitis
	Retinitis
	Uveitis
	Vitritis
Visual acuity reduced	Visual acuity reduced

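### SAP 2.1 defines the primary safety outcome by measurements but identifies events through an ungraded adverse event term list, with no rule joining the two

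*SAP*

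**What the plan says.** SAP 2.1 lists five components. Each must occur within 6 weeks of administration and be at least possibly related to the ATIMP rather than to surgery alone. Two rest on measurements:

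- Acuity: "Reduction in visual acuity by 15 Early Treatment Diabetic Retinopathy Study (ETDRS) letters or more".
- Inflammation: "Severe unresponsive inflammation (defined in Section 4.2 of the protocol"). Protocol 4.2.1 gives three alternative signs, starting with "anterior chamber cells 3+ (26-50 cells in a field size of 1mm x 1-mm slit-beam), or"; the others are flare of 3+ and vitreous haze of 3+. The sign must also fail to improve by two steps, or to grade 0, over 6 weeks.

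SAP 2.1 then closes with "The adverse events preferred terms are identified in Attachment 2". The attachment is headed "LIST OF ADVERSE EVENT PREFERRED TERMS FOR THE PRIMARY SAFETY OUTCOME".

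SAP 5.1 reports the proportion of participants with the outcome and a 95% interval, by age group, dose level and overall, plus a listing. As data sources, visual acuity and ocular examination are itemised only in SAP 2.2, where "the following efficacy outcomes will be analyzed or summarized depending on the amount of data collected".

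**The concern.** A criterion stated in letters and slit-lamp grades needs a derivation from letters and grades. The SAP gives a list of coded terms and does not say whether a listed term is sufficient, necessary, or only a prompt to look at the measurements. Two programmers could follow the text and produce different primary results. The result could then depend on how an investigator words an event and how it is coded. With cohorts of 3, and an interval that Protocol 5.10.3.2 intends as an upper bound on the event rate, one participant matters.

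**Working it through.** The documents give no event rate, power or sample size for this outcome, so there is no figure to reproduce. The check is a comparison of texts, followed by arithmetic for scale.

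**Step 1. Criterion against list.**

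| Component | Criterion (SAP 2.1, Protocol 4.2.1) | Attachment 2 |
|---|---|---|
| Acuity | Loss of 15 or more ETDRS letters | One term, *Visual acuity reduced*; no letter count, no eye |
| Inflammation | SUN 3+ cells, flare or vitreous haze, without 2-step improvement (or to grade 0) in 6 weeks | 19 terms, including *Anterior chamber cell* and *Anterior chamber flare*; no grade or duration; vitreous haze has no term of its own, though *Vitritis* may catch some cases |
| Endophthalmitis | Infective only | *Endophthalmitis*, unrestricted, and the same term again under inflammation |
| Ocular malignancy | Presence | Malignancy terms |
| Non-ocular SUSAR | Grade III or above | No entry |

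**Step 2. If a listed term is sufficient.** Any possibly ATIMP-related cells or flare would count, at any grade. Protocol 5.4.2.3(i) says "A temporary intraocular inflammatory response is expected following vitrectomy surgery" and that it can reach 2+ cells, which is below the 3+ threshold.

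**Step 3. If a listed term is necessary.** A possibly related 15-letter loss recorded under its cause, and so coded to another term, does not pass.

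**Step 4. Can the adverse event record supply the threshold?** No. Protocol 5.11.3.5.2 grades severity by CTCAE, which is neither the SUN scale nor a letter count.

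**Step 5. Are the measurements planned?** Yes. Protocol Table 2 schedules acuity and ocular examination at D1, D3, W1, W2, W4 and W6, and again at W12 and W24.

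**Step 6. Effect of one misclassified participant.** The SAP 5.1 interval is p ± [1.96·√(p(1−p)/n) + 1/(2n)], cut to 0–1, with p = x/n. I take n = 3 (one cohort) and n = 18 (the stated maximum). Exact (Clopper-Pearson) limits are given for comparison.

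| x/n | Proportion | SAP interval | Exact interval |
|---|---|---|---|
| 0/3 | 0% | 0 to 16.7% | 0 to 70.8% |
| 1/3 | 33.3% | 0 to 100% | 0.8 to 90.6% |
| 0/18 | 0% | 0 to 2.8% | 0 to 18.5% |
| 1/18 | 5.6% | 0 to 18.9% | 0.1 to 27.3% |

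For 1/18 the half-width is 1.96·√(0.0556·0.9444/18) + 1/36 = 0.106 + 0.028 = 0.134, so the upper limit is 0.056 + 0.134 = 0.189.

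**Step 7. Chance of a false count if terms alone decided.** Let q be the probability that a participant without a true event carries a possibly ATIMP-related mild inflammation term. The documents give no q; the range below is an assumption, with participants taken as independent. P(at least one false count) = 1 − (1 − q)^n.

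| q | n = 3 | n = 18 | Expected false counts in 18 (18q) |
|---|---|---|---|
| 0.05 | 0.14 | 0.60 | 0.9 |
| 0.10 | 0.27 | 0.85 | 1.8 |
| 0.20 | 0.49 | 0.98 | 3.6 |
| 0.30 | 0.66 | >0.99 | 5.4 |

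**The case against.** A reader might infer that the term list replaces the measurements. The documents do not say so. SAP 2.1 keeps the letter and severity criteria, and the sentence on terms follows them without displacing them. The list has no entry for the SUSAR component, so it cannot be the complete case definition. The defect is an unspecified link, not a documented substitution, and it would be wrong to say that two components are certain to be misclassified.

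Further points in the plan's favour:

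- **Relatedness.** Inflammation due to surgery alone is excluded, and Protocol 5.11.3.5.3 asks for separate causality for surgery and ATIMP. This stands as a limit on false counts. Separating the two causes in the first weeks is still a judgement, and possibly related is a low bar.
- **Reporting of test results.** Protocol 5.11.3.5 requires clinically significant abnormalities of objective tests to be recorded as adverse events, so a 15-letter loss may have its own record. The safeguard depends on that judgement of significance and on the term chosen. Protocol 5.11.3.5.4 lists an acuity decrease of up to 8 weeks as expected with surgery, which is longer than the 6-week window, so non-reporting or attribution to surgery alone is plausible.
- **Surgical causes.** Retinal detachment, intraocular haemorrhage and lens opacity are expected surgical events. A loss from one of these would often be excluded correctly, so they are weak examples of missed cases.
- **Double listing.** *Endophthalmitis* appears twice, but a participant cannot be counted twice in an any-event outcome.
- **Separate programming document.** SAP section 1 mentions one, and it may hold the derivation. It was not available for this review. The same section says the SAP itself specifies key derived variables, and the primary outcome is one.
- **Limited use.** The analysis is descriptive, cases are listed individually, and dose escalation rests on SDMC review against the protocol's own definition. That lowers the consequence for escalation but leaves the reported primary result undefined.

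**Conclusion.** The point holds as a gap in specification. The SAP states measured criteria, points to ungraded terms, and gives no rule for combining them. Either simple use of the list can misclassify: as case definition it admits possibly ATIMP-related inflammation below 3+, and as filter it drops a possibly related acuity loss coded elsewhere.

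One error moves a cohort of 3 between 0% and 33%. In 18 participants, missing a single true event would lower the upper limit of the SAP interval from 18.9% to 2.8% (exact: 27.3% to 18.5%). How often such errors would occur cannot be read from the documents; the probabilities in Step 7 rest on assumed values of q and apply only if terms alone decide cases. The conclusion also assumes that no derivation exists in the separate programming document. It should be settled before the outcome is programmed.

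**What to change.** In SAP 2.1 and 5.1:

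1. Derive the acuity component from treated-eye ETDRS letters against baseline, and state which baseline applies. SAP 3.2 uses the closest prior visit in general but a mean for efficacy parameters with several baseline assessments.
2. Derive the inflammation component from recorded SUN grades over time, including the non-improvement condition.
3. Then apply relatedness from the adverse event linked to that finding, whatever its preferred term.
4. Use Attachment 2 only as a cross-check that triggers review of the measurements.
5. Limit the endophthalmitis component to events recorded as infective.

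Before programming, reconcile the acuity criterion. SAP 2.1 calls its criteria the same as the dose-limiting event but omits the condition in Protocol 4.3.2.1 and 5.5.1 that the loss fails to resolve to within 15 letters of baseline in a 4-week period. The passages must agree, because a visit-by-visit comparison without a resolution condition would flag transient early losses, including D1 and D3 readings taken with the previous refraction.

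The cost is SAP wording and programming on assessments already scheduled. This assumes that the eCRF, which was not available, holds the letters and SUN grades. The small downside is that each qualifying measurement must be linked to an adverse event record for causality.
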